symptom severity) women will be assigned to either weekly vitamin D₃ supplementation of 50,000 IUs or 5000 IUs for a period of six months. Since guidelines recommend assessing vitamin D levels at three months upon initiating this dose, study measurements will be collected at baseline, three, and six months. The following outcomes will be measured: depressive symptoms, diabetes self-management (self-efficacy, diabetes distress, diabetes self-care behaviors), and systolic blood pressure. We will also explore a possible mechanistic effect of vitamin D₃ supplementation on depression. Evidence indicates that in depression, pro-inflammatory biomarkers, notably cytokines and C-reactive protein (CRP), are elevated (45-48). Several studies (not depression studies) have reported that Vitamin D can decrease levels of inflammatory biomarkers (49-51). Thus we will explore whether vitamin D₃ supplementation decreases inflammatory biomarkers (CRP, interleukin-6, and tumor necrosis factor- α) providing evidence for a possible mechanism of antidepressant activity.

Aim 1: To determine the effect of 50,000 IUs of vitamin D₃ supplementation on depressive symptoms (primary outcome), self-management (secondary outcome), and systolic BP (exploratory outcome) compared to 5000 IUs.

Hypothesis: Women receiving 50,000 IUs of vitamin D₃ supplementation will report fewer depressive symptoms, increased diabetes self-management mediated by depression improvement, and have a lower systolic BP compared to those taking 5000 IUs at three and six months follow-up.

Aim 2: To explore the mechanistic effect of vitamin D supplementation on inflammatory biomarkers and their association with depression.

Hypothesis: Women receiving 50,000 IUs of vitamin D₃ supplementation will have a decrease in inflammatory biomarkers which will be associated with fewer depressive symptoms compared to those taking 5000 IUs at three and six months follow-up.

UPDATED AIMS

A sub-study was added to investigate family functioning in women with Diabetes and Depression titled *Family Matters in Diabetes and Depression (FAMDD)*. This study is also funded under LU# 208808
This sub-study of the Sunshine 2 Study has the following specific aims and hypotheses:

Aim 1: Describe the impact of family functioning on self-management, barriers to self-management, and FQOL in women with depression and T2DM. (qualitative)

Aim 2: Determine the relationship of depressive symptoms, family functioning and FQOL.

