Hypothesis 1: Women receiving 50,000 IUs vitamin D supplementation will report fewer depressive symptoms (primary outcome), increased diabetes self-management mediated by depression improvement (secondary outcome), and have a lower systolic BP (exploratory) compared to those 5000 IUs at three and six months follow-up.

For analysis of the primary outcome (depressive symptoms) generalized, linear, mixed models (GLMM) for repeated measures will be used (154). The proposed model will have one between-subjects variable GROUP (vitamin D supplementation; control) with two levels and one within-subjects variable TIME with three levels (baseline, 3 and 6 months). The test of the hypotheses will hinge on the GROUP by TIME interaction as an indication of group differences in the variable of interest over time. A given hypothesis will be supported with the finding of a statistically significant GROUP by TIME interaction, and the finding that the means are in the hypothesized direction. GLMM will be implemented using SPSS which will provide estimates of the means for each outcome variable by time and treatment groups. The results will be summarized with adjusted means and 95% confidence intervals. A compound symmetric covariance structure will be assumed. If necessary, other covariance structures, such as Huynh-Feldt, will be investigated. An intention-to-treat analysis (ITT) which includes an analysis of completers and noncompleters will also be done using GLMM. Stratification by depression severity should provide comparable groups at baseline; however, differences will be assessed. All analyses will control for baseline values of body composition (body fat), race (white compared with nonwhite), and time at entry into the study (as season of the year, winter, summer, spring, fall) as previously done by our consultant, [name], in his vitamin D trials. Other covariates, related to diabetes (length of time with diabetes, HBA1c), lifestyle factors, (physical activity, diet), and previous depression will be added to generate a multivariate model which is parsimonious and based on the clinical relevance and statistical significance of these factors.

For analysis of the secondary outcome (self-management), regression analysis will be used to test whether an improvement in self-management is mediated by an improvement in depressive symptoms (Figure). The Preacher and Hayes macro add-on for SPSS will be used. This technique estimates the path coefficients and

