generates bootstrap confidence intervals for total and specific indirect effects of the independent variable (vitamin D supplementation) on the dependent variable (diabetes self-management) through one or more mediator variables (depressive symptoms). This method allows for testing indirect effects through a mediating variable without the estimation of a direct link between independent variable on an outcome, and also adjusts for the potential influence of covariates (155, 156).

For the exploratory outcome (blood pressure), GLMM will be used to examine for the direct effect of vitamin D on blood pressure since there is physiologic evidence to support this. The GLMM statistical procedures described above will be used.

Hypothesis 2: Women receiving 50,000 IUs vitamin D supplementation will have a decrease in inflammatory biomarkers which will be associated with fewer depressive symptoms compared to 5000 IUs at three and six months follow-up.

For this exploratory hypothesis, to determine if there is a decrease in the inflammatory markers, the same procedures (GLMM) will be used. If significant, then correlational methods (parametric and non-parametric) will be used to explore the association between vitamin D supplementation, depression, and the inflammatory biomarkers.

1. For the sub-study FAMDD, the qualitative component (**Aim 1**) interview data is being transcribed.

Following transcription, there will be verification of the transcription by [name]. Once these data have been verified, a narrative analysis will be conducted. Narrative inquiry was chosen to focus on the relationship between individuals' life stories and it guides synthesis of data to represent the participants' stories as a whole. Particular modifiable factors that mitigate health risks for family members and factors that facilitate self-management will be identified. Study team involved in this component of qualitative analysis includes [name], [name], [name] and [name].

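### Aim 2 examines the biomarker–depression link by correlations run only after a significant biomarker result and with no stated conditioning on arm, so two separate dose effects could be read as a mechanism

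*Combined protocol and SAP*

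**What the plan says.** Aim 2 in the opening section is "To explore the mechanistic effect of vitamin D supplementation on inflammatory biomarkers and their association with depression". Hypothesis 2, as restated in V.5.b Data Analysis, is that women on 50,000 IUs "will have a decrease in inflammatory biomarkers which will be associated with fewer depressive symptoms compared to 5000 IUs at three and six months follow-up". It therefore has two parts: a dose effect on the markers, and an association of that decrease with fewer depressive symptoms.

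V.5.b handles the parts in sequence, introduced by "For this exploratory hypothesis". For the first: "to determine if there is a decrease in the inflammatory markers, the same procedures (GLMM) will be used". Those procedures are the ones given for the primary outcome, where "The test of the hypotheses will hinge on the GROUP by TIME interaction". For the second: "If significant, then correlational methods (parametric and non-parametric) will be used to explore the association between vitamin D supplementation, depression, and the inflammatory biomarkers".

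Three other statements bear on this:

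- The adjustment rule for the primary study in V.5.b reads: "All analyses will control for baseline values of body composition (body fat), race (white compared with nonwhite), and time at entry into the study". Season of the year defines the time at entry. Treatment arm is not in the list.
- V.5.b plans a bootstrap indirect-effect analysis, with supplementation as the independent variable, for self-management. It plans none for the biomarkers.
- V.5.a Data Management plans Pearson and Spearman correlations among variables as a preliminary look. These depend on no earlier test, and no conditioning on arm is stated for them either.

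The plan does not say whether the Aim 2 correlations use levels or changes, or which visit.

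**The concern.** Hypothesis 2 expects the high dose to lower both the markers and CES-D. When two outcomes both differ by arm, they correlate across the whole sample even if they are unrelated among women on the same dose. An analyst who follows the sentence as written can correlate marker and CES-D over all women and obtain a positive coefficient made up only of two parallel arm effects. That coefficient points in the hypothesized direction, and the stated purpose of the aim is mechanism.

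The significance condition has two consequences. It retains trials in which the observed arm difference in the marker is larger, and so the induced correlation is larger. It also means that a marker without a significant result gets no planned test of the association half of Hypothesis 2.

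**Working it through.** **The plan's own figure.** V.5.d Sample Size Estimation states 85% power for inflammation at 75 per group and gives no effect size. The TNF-alpha pilot values (section IV: 2.15 ± 0.04 in 48 depressed patients, 1.59 ± 1.59 in 23 controls), with ± read as SD and the variances averaged, give d = 0.56 / √((0.04² + 1.59²)/2) = 0.56/1.125 = 0.498. Power at 75 per arm is then 86%, close to the stated figure. Conversely, 85% power implies d = (1.960 + 1.036) × √(2/75) = 0.489. Other readings of the pilot values do not match. The power is for group differences, not for the association. The pilot contrast is depressed versus healthy people, not a treatment effect.

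**Inputs**

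- 75 per arm, 150 in total, two-sided 0.05 (V.5.d).
- CES-D effect: 0.46 as stated in V.5.d; or 7 points (14 versus 7) over the pilot six-month SD of 8.3, which is 0.84. The plan does not show how 0.46 was obtained, so both are used.
- Marker effect: 0.49, an assumption back-solved from the 85% power; range 0.3 to 0.8.
- Within-arm correlation: zero, by assumption.

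**Induced correlation.** With 1:1 allocation and no within-arm link,

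r = (d₁d₂/4) / √[(1 + d₁²/4)(1 + d₂²/4)].

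- Marker 0.49, CES-D 0.46: 0.0564 / √(1.0600 × 1.0529) = 0.053.
- Marker 0.49, CES-D 0.84: 0.1029 / √(1.0600 × 1.1764) = 0.092.

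Significance at n = 150 needs |r| ≥ 1.976/√(148 + 1.976²) = 0.160. Both effects must be about 0.88 SD before the expected induced r reaches that value.

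**False-positive rates.** 20,000 simulated trials per row, with normal data, equal variances and one value or change score per woman. A two-sample t-test on the marker stands in for the GROUP by TIME test. The pooled Pearson test is compared with the partial correlation given arm.

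| Marker d | CES-D d | Induced r | Condition met | Pooled, all trials | Pooled, after condition | Arm-adjusted, after condition |
|---|---|---|---|---|---|---|
| 0.3 | 0.46 | 0.033 | 45% | 6.8% | 8.4% | 5.1% |
| 0.3 | 0.84 | 0.057 | 45% | 11.2% | 17.3% | 4.8% |
| 0.49 | 0.46 | 0.053 | 85% | 9.9% | 10.5% | 4.7% |
| 0.49 | 0.84 | 0.092 | 84% | 20.2% | 22.7% | 5.2% |
| 0.8 | 0.46 | 0.083 | 99.8% | 17.3% | 17.3% | 5.1% |
| 0.8 | 0.84 | 0.144 | 99.8% | 42.5% | 42.5% | 4.6% |

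**Effect of the condition.** At a marker effect of 0.49 it adds little: 9.9% to 10.5%, or 20.2% to 22.7%. It matters more with a weak marker effect and a strong CES-D effect: 11.2% to 17.3%. At a marker effect of 0.3, a single marker misses the condition in 100 − 45 = 55% of trials. For three markers at that effect, if independent, all miss in 0.55³ = 17%.

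**The case against.** The strongest reply is that the text leaves the method open rather than choosing a wrong one. It speaks of correlational methods, names supplementation among the variables, and sits under a general rule to control for covariates. A partial or within-arm correlation would be compatible with it. A reader might infer that the plan prescribes a pooled correlation with no arm term; the documents do not say that. What stands is that no conditioning on arm is specified, and naming supplementation as a third variable does not condition the other two on it.

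The sequence is also defensible. Hypothesis 2 concerns a decrease that is then associated with symptoms, and following up only the markers that moved is a recognisable exploratory strategy. A reader might infer from the 55% figure that Aim 2 would usually go unanswered. That figure is for one marker at an assumed effect, and at least three markers are named. V.5.a also plans unconditional preliminary correlations, so the association would not go wholly unexamined. Those correlations are a data check with no stated arm adjustment, so they do not replace the Aim 2 test.

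Finally, the aim is labelled exploratory and no confirmatory claim rests on it. That limits the consequence, but a pooled correlation still cannot separate a mechanism from two parallel effects.

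**Conclusion.** The point holds as a minor one. Aim 2 specifies no conditioning on arm for the biomarker–depression pair, and it withholds the planned association test from any marker that misses significance. At the stated CES-D effect of 0.46 and the assumed marker effect of 0.49, a pooled analysis roughly doubles the nominal 5% error. With a CES-D effect of 0.84 it reaches about 23%. Adjusting for arm restores 5% throughout.

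A reader might go further and say that two independent effects would appear as a mechanism. The figures do not support that: at the stated CES-D effect about 89% of trials meeting the condition show no significant pooled correlation, and at 0.84 about 77% show none. A reader might also divide 7 points by the pilot baseline SD of 7.6, obtain 0.92, and treat it as the plan's effect size; the effect size that the plan states is 0.46.

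The results rest on real dose effects on both CES-D and the marker, no within-arm association, normal data with equal variances, and a t-test in place of the repeated-measures test. The documents give no treatment effect on any marker, so the rates should be read across the range shown.

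**What to change.** In V.5.b, Hypothesis 2, remove the significance condition and replace the correlation sentence with one model per marker: regress six-month CES-D change on six-month marker change, with arm and the baseline values of both in the model. Use a rank-based version for skewed markers. Report the coefficient and its interval whatever the mixed model shows, and label it an exploratory, non-randomised association, because arm adjustment does not remove other shared causes of marker and mood.

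The cost is SAP wording and one extra model per marker, on data already planned for collection. The downside is a few more exploratory tests: with three markers, if independent, the chance of at least one false positive is 1 − 0.95³ = 14%, which the report should acknowledge.

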In this repeated measures study (baseline, 3, and 6 months), a linear mixed effects model will be used to estimate the effect of FUM on patients' LUTS severity score while allowing random intercepts for each participant to account for the within subject correlation engendered by the repeated measurements. Since we are documenting UTIs over the trial, we will also explore the odds of experiencing at least one UTI, to be estimated as a function of the FUM using a generalized linear mixed effects model that also allows random intercepts for each participant; a binomial distribution with logit link will be specified to determine the odds ratio for the FUM diversity index and microbial taxa count. In these models, extreme error variances will be monitored using the ratio of the Pearson chi-square fit statistic over its degrees of freedom. When necessary, UTI may be treated as a count variable

(particularly if there are enough participants experiencing multiple UTI events) and a Poisson distribution with negative binomial link may be used to adjust for observed overdispersion.

(2) To determine the impact of glycemic control on the LUTS and FUM composition in women with T2DM.

Hypothesis: In women with T2DM, the effect of FUM on LUTS *depends* on glycemic control (HBA1C), which may be measured as a continuous or binary (i.e., >7% versus ≤ 7%) variable.

Planned Analyses: Testing this hypothesis is largely a continuation of the investigation specified in prior objective, except that each model will evaluate if any effect of the FUM on LUTS severity *depends* on women's level of glycemic control. Consequently, for this aim, an interaction term between FUM and glycemic control will be estimated for each model specified above. If the interaction is not significant, adjusted estimates will be provided for the effect of FUM on LUTS after controlling for the effect of glycemic control, as well as other salient covariates (e.g., race, age, depression level, body mass index, and concomitant medications).

For both hypotheses, all comparisons, including all possible pairwise interaction terms, will be evaluated using an alpha level of 0.05 and the tests will be two tailed, meaning that an effect in either direction will be interpreted.

Secondary Objective:

To determine whether there is an association between vitamin D status (sufficient, insufficient, and deficient), LUTS, and the FUM.

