Hypothesis (a): Women with T2DM who have less vitamin D will have will have a different FUM composition than those with sufficient vitamin D.

Hypothesis (b): Women with T2DM who have less vitamin D will have will have more LUTS than those with sufficient vitamin D.

Planned Analyses: For this secondary objective, a generalized linear mixed effects model will be used to determine the odds of at least one UTI as a function of ordinal vitamin D status (deficient, insufficient, and sufficient), again allowing random intercepts for each participant to account for within subject correlation due to repeated measurements; these models will specify a binomial distribution with logit link to determine the odds ratio for each pairwise comparison of vitamin D status. As before, extreme error variances will be monitored using the ratio of each model's Pearson chi-square fit statistic over its degrees of freedom. When necessary, a negative binomial link may be used to account for observed over-dispersion. Finally, a linear mixed effects model will be used to estimate the effect of ordinal vitamin D status on patients' FUM indices and microbial taxa count as well as their LUTS symptom severity score, again allowing random intercepts for each participant. For this objective, all model terms will be evaluated using an alpha level of 0.05 and the tests will be two tailed, meaning that an effect in either direction will be interpreted.

To compare vitamin D, LUTS and the FUM, each individual will function as her own control, with the first time point establishing the baseline FUM profile with which to compare the effect of treatment dose at 6 months (endpoint of trial). We will model the outcome using a GLMM, which takes into account the correlation between 2 observations on the same woman. We will determine if there is a change in a women's FUM baseline to end of study by treatment. We will use similar procedures to determine treatment group differences. Similar data analyses will be conducted on the urinary symptoms reported by each participant across time points and between groups.

Exploratory Aim: To examine the relationship of the phage activity with glycemic control, other labs including Urine PH in biobanked urine samples in the laboratory of [name].

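### The urinary microbiome sub-study names a negative binomial link as the remedy for overdispersion: it does not correct the variance of UTI counts and does not apply to the 0/1 UTI outcome

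*Combined protocol and SAP*

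**What the plan says.** The point concerns V.5.b Data Analysis, sub-study on the Urinary Microbiome.

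**Primary Objective 1.**
- The main UTI outcome is binary and exploratory: "we will also explore the odds of experiencing at least one UTI".
- The model is a "generalized linear mixed effects model that also allows random intercepts for each participant", and "a binomial distribution with logit link will be specified to determine the odds ratio for the FUM diversity index and microbial taxa count".
- The check on fit is that "extreme error variances will be monitored using the ratio of the Pearson chi-square fit statistic over its degrees of freedom". No trigger value is given.
- A count version is a fallback: "When necessary, UTI may be treated as a count variable". For that version, "a Poisson distribution with negative binomial link may be used to adjust for observed overdispersion".

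**Secondary Objective.** At least one UTI is modelled on vitamin D status with a binomial distribution, logit link and random intercept, and odds ratios are reported for each pairwise comparison of status. The same Pearson check is applied. Then: "When necessary, a negative binomial link may be used to account for observed over-dispersion". No distribution is named to go with that link.

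Under both objectives, terms "will be evaluated using an alpha level of 0.05 and the tests will be two tailed". Neither names a negative binomial distribution, a scale parameter or robust standard errors.

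**The concern.** In a generalized linear model the link connects the mean to the linear predictor, and the distribution supplies the variance. Overdispersion means that the variance exceeds what the distribution allows. The plan changes the link, so its remedy acts on the wrong part of the model. It would be invoked only after excess variance had been seen, and would leave that excess in place.

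Two things are at stake. In the count analysis, confidence intervals and p-values for the FUM could be too optimistic. In the binary analysis, replacing the logit link means that the coefficients no longer yield the odds ratios that the objective asks for.

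**Working it through.** **Inputs.** From the plan: two-sided alpha 0.05; visits at baseline, 3 and 6 months; a random intercept per participant. The plan gives no UTI rate, dispersion, power or sample size for these analyses, so there is no figure to reproduce. Assumed for illustration: 150 women (the main trial's final sample in V.5.d), a mean μ of 0.5 to 1 UTI per observation, and an extra-variance parameter *a* of 1 to 2.

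**1. Variance.** With a Poisson distribution, Var(Y) = μ whatever the link. With a negative binomial distribution, Var(Y) = μ + aμ² = φμ, where φ = 1 + aμ. If the truth is φμ and the model uses μ, then model SE / true SE = 1/√φ, and actual alpha = 2[1 − Φ(1.96/√φ)].

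| φ | SE ratio | actual alpha |
|---|---|---|
| 1.2 | 0.91 | 0.074 |
| 1.5 | 0.82 | 0.110 |
| 2 | 0.71 | 0.166 |
| 3 | 0.58 | 0.258 |

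**2. Does the link help?** Independent counts, null covariate, no random intercept, 600 runs per row. Entries are type I error (model SE / empirical SD).

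| μ, a (φ) | Poisson, log link | Poisson, negative binomial link | Negative binomial, log link |
|---|---|---|---|
| 0.5, 1 (1.5) | 0.088 (0.85) | 0.117 (0.84) | 0.045 (1.04) |
| 0.5, 2 (2) | 0.157 (0.69) | 0.175 (0.66) | 0.045 (0.97) |
| 1, 1 (2) | 0.170 (0.70) | 0.167 (0.69) | 0.047 (0.99) |

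The literal specification can be fitted, and it does no better than the ordinary log link. Changing the distribution does repair the error. This table isolates the link; it is not the planned mixed model.

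**3. With the planned random intercept.** Poisson, log link, three visits, 200 runs per setting (Monte Carlo error about 1.5 points near 5%):

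| Source of extra variation | Covariate | Type I error | SE ratio |
|---|---|---|---|
| Between women (log-normal) | either kind | 0.04 to 0.05 | 0.99 to 1.04 |
| Visit level | constant within woman | 0.03 to 0.055 | 1.01 to 1.07 |
| Visit level | changes by visit | 0.07 to 0.105 | 0.79 to 0.89 |

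A separate check of the last row, with means 0.5 to 1 and gamma dispersion 1 to 2, gave about 12% to 25%. The answer depends strongly on the assumed mean and dispersion, so about 7% to 25% is an illustration, not an estimate for this study. One coarser run (15 integration nodes, gamma between-woman variation) gave 0.20 for a covariate constant within a woman. It was set aside as probably due to coarse integration and misfit of the random-effect distribution; the rerun changed both, so their effects were not separated.

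**4. The binary outcome.** A single 0/1 record has variance p(1 − p), fixed by its mean, so it cannot be overdispersed. Simulated with heterogeneous risk, the logistic model gave Pearson/df 1.01 and type I error 0.053. Reading the sentence as a negative binomial distribution does not help either. With dispersion 1 its variance is p + p² against a true p − p²:
- p = 0.2: 0.24/0.16 = 1.5, so SEs are √1.5 = 1.22 times too large.
- p = 0.4: 0.56/0.24 = 2.33, so SEs are √2.33 = 1.53 times too large.

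Simulation agreed (1.19 and 1.51 times), with rejection rates of 1.9% and 0.1%, against 5.1% and 4.6% for the logit model. The error there is in the conservative direction.

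**The case against.** **It is a slip of terminology.** Both sentences pair negative binomial with overdispersion, and the authors very probably mean negative binomial regression. If the count model is fitted that way, the standard-error problem disappears. This is a fair reading of intent, but the plan names Poisson as the distribution in one place and no distribution in the other, and the literal version can be run. The reading also does not rescue the 0/1 outcome (step 4).

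**The random intercept deals with it.** This stands for variation between women. With one gamma-Poisson count per woman, plain Poisson rejected in 13% to 28% of runs and Poisson with a random intercept in 3.8% to 7.3%. It does not stand for visit-level variation when the exposure also changes by visit, as the FUM can. The Pearson check is applied to models that already contain the intercept, so a remedy triggered by it concerns what the intercept left over. The plan implies, but does not state, that the count version keeps the intercept.

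**The Secondary Objective sentence may be shorthand for the count fallback.** The Pearson check there refers back to the preceding analyses, so this is possible. For that reason the fix allows the sentence to be restricted to counts instead of deleted.

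**The stakes are small.** This stands. The UTI analysis under Primary Objective 1 is exploratory and the count model is optional.

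**Stronger readings.** A reader might infer that all UTI tests have standard errors that are too small, or that associations with vitamin D status would be declared too often. The documents do not support either: the specified UTI outcome is binary, and the Secondary Objective names no count or Poisson model. A reader might also quote a type I error of 10% to 25% from a simulation with one count per woman and no random intercept. That is not the planned model.

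**Conclusion.** The remedy is wrong as written in both places, with narrow consequences.

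- **Count fallback, Primary Objective 1:** a Poisson distribution with a negative binomial link leaves visit-level overdispersion uncorrected, so standard errors for time-varying exposures such as the FUM would be too small. The participant intercept absorbs between-woman overdispersion, provided it is kept in the count model. The size cannot be derived from the documents; the simulated rates rest on assumed means, dispersions and 150 women.
- **Binary outcome, Secondary Objective:** the remedy does not apply. Used literally, it gives up the odds ratio. The fault is an inapplicable model, not understated standard errors.
- **Elsewhere:** the primary CES-D analysis and the linear mixed models for LUTS severity and FUM indices do not use this remedy and are unaffected.

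It is worth correcting because the rule would be applied after the data had shown a problem, when an unambiguous prior specification is most useful.

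**What to change.** **Primary Objective 1:** state that, if UTI is analysed as a count and Pearson chi-square/df shows overdispersion, the model will use a negative binomial distribution with log link, keep the participant random intercept, and report rate ratios. It would help to state the Pearson/df value that triggers the switch, since none is given.

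**Secondary Objective:** keep the binomial distribution, logit link and random intercept for at least one UTI. Delete the negative binomial sentence, or restrict it to the count analysis defined under Primary Objective 1.

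**Cost:** a wording change in the analysis section. No change to data collection or sample size is needed.
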